3.1.7 Methods of Pooling Data

Because of the large number of centers relative to the number of subjects, an analysis adjusted by study center is not planned. Similarly, it is not expected to have a sufficient number of subjects in each country involved in the study to adjust for country. However, descriptive analysis will be performed by country for the primary efficacy endpoint.

3.1.8 Analysis Visit Windows

Visit windows for study conduct are specified in Table 1: Schedule of Activities. Unless otherwise specified, the following analysis visit rules will be implemented for all endpoints [REDACTED] and seizure diary (see sections 3.8.3, 3.8.4, and 3.9.6 for analysis visit window computations). For all unscheduled visits and end of treatment (EOT) visits from subjects discontinuing treatment early (before Week 12), assessments will be mapped according to the analysis visit windows in Table 2 for primary summarization and analysis. If the visit does not fall within any of the analysis visit windows, then the visit will be considered missing at the specified time point for analysis purposes.

Table 2: Nominal (Targeted) Time Points and Analysis Visit Windows

Assessment	Nominal (Targeted) Time Point	Analysis Visit Window (Interval in Study Days)
Baseline Assessments	Study Day 1	≤ Day 1
Phone/Titration (Day 6)	Study Day 6	>Day 1 - ≤Day 8
Phone/Titration (Day 11)	Study Day 11	≥Day 9 - ≤Day 21
Week 6 (Study Day 43)	Study Day 43	≥Day 22 - ≤Day 64
Week 12 (Study Day 85)	Study Day 85	≥Day 65 - ≤Day 92
Week 14 (Study Day 99)	Study Day 99	≥Day 93

After mapping the data from unscheduled and end of treatment (EOT) visits from subjects discontinuing treatment early to the nominal time point, the following rules will apply if multiple records are available within a single analysis visit window unless otherwise specified for a particular analysis:

- If a record exists for the nominal time point, that record will be selected for analysis.
- If a record for the nominal time point does not exist and multiple records are available within a single analysis visit window,
 - The record closest to the planned assessment day will be selected for analysis
 - If 2 records are equidistant from the target day, then the earliest record will be selected (does not apply to the Week 12 or 14 visits).
- If a subject has no record in an analysis window, the subject will be considered missing at that time point.

For the primary and key secondary objectives, a supportive analysis will be conducted in which CGI-I-AS assessments from unscheduled visits and end of treatment (EOT) visits from subjects discontinuing treatment early (before Week 12) will be mapped according to the analysis visit windows in Table 3.

Table 3: Nominal (Targeted) Time Points and Alternative Analysis Visit Windows

Assessment	Nominal (Targeted) Time Point	Analysis Visit Window (Interval in Study Days)
Baseline Assessments	Study Day 1	≤ Day 1
Week 6 (Study Day 43)	Study Day 43	>Day 1 - ≤Day 43
Week 12 (Study Day 85)	Study Day 85	>Day 43

After mapping the data to the nominal time point, the following rules will apply if multiple records are available within a single analysis visit window unless otherwise specified for a particular analysis:

- If a record exists for the nominal time point, that record will be selected for analysis.
- If a record for the nominal time point does not exist and multiple records are available within a single analysis visit window,
 - The record closest to the planned assessment day will be selected for analysis
 - If 2 records are equidistant from the target day, then the earliest record will be selected (does not apply to the Week 12 visit).
- If a subject has no record in an analysis window, the subject will be considered missing at that time point.

In addition, for the primary and key secondary objectives, an additional supportive analysis will be conducted in which CGI-I-AS assessments will be analyzed according to the nominal visit time point (i.e. only records identified as baseline and records from the Day 43/Week 6 and Day 85/EOT/Week 12 visits will be included).

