For each subject, after informed consent is obtained, screening assessments will be completed within the 28 days preceding Day 1 (baseline). On Day 1, each subject who meets all eligibility criteria will receive the first assigned blister cards of study drug capsules according to the treatment code (except for subjects 2 to 3 years old, who will receive study drug capsules in bottles), sufficient to last until the Week 6 visit, when blister cards (or bottles for ages 2 to 3 years) will be collected and unused study drug will be counted. Study drug will be similarly dispensed at the Week 6 visit, and blister cards (or bottles for ages 2 to 3 years) will be collected and unused study drug will be counted at the Week 12 visit. Caregivers/LARs will be provided an additional blister card in case of unexpected delays for study visits (e.g., inclement weather/flight delays).

The LAR/caregivers will complete paper seizure diaries on behalf of subjects throughout the study, from issuance during screening (and at study visits) through Week 12 (EOT).

Safety information will be collected during phone calls on Day 6 and Day 11 and during the EOS visit, as well as during every study site visit. Each subject's LAR/caregiver will be instructed to contact the study center if the subject experiences any adverse events (AEs), is unable to take the study drug as prescribed, [REDACTED]

At the investigator's discretion throughout the study, subjects may be evaluated at unscheduled clinic visits for reasons related to subject safety. At unscheduled visits, subjects will be queried about AEs and changes in concomitant medications and evaluated for suicidality. Safety laboratory assessments may be conducted. Periodic interim review of safety data will be performed by the IDMC and as part of routine pharmacovigilance activities.

Estimated Study Duration:

[figure not shown]
After informed consent is obtained, screening assessments will be conducted within the 4 weeks preceding baseline, followed immediately by treatment for 12 weeks and a 2-week follow-up period (for subjects not enrolling into the ELARA study), for a maximum duration of individual subject participation of 18 weeks. Four study site visits are scheduled for each subject.

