- In the absence of a telehealth system, a remote assessment is to be completed by utilizing a unified communication software such as Skype, Microsoft Teams or Zoom
- Provide a script to a local lab as required per clinical labs per protocol
- Home visits may be conducted by a trained mobile healthcare professional to perform study assessments e.g. vital signs, body system assessment, clinical labs draws, review/collection of study materials
- If the site visits become possible/permissible at any point between Week 6 and Week 12, the subject should be scheduled for an on-site, unscheduled visit prior to week 12 time point and all safety assessments should be completed at this visit
- IP with kit number will be assigned to each subject. Where allowed, a preferred courier will be assigned to pick up and deliver the IP to subject.

Guidance established subjects completing Week 12 Study Visit

- Whenever possible, all week 12 visits should be completed onsite
- If an onsite visit is not possible, a remote visit should be completed to collect assessments via telehealth system. A unified communication software such as Skype, Microsoft Teams or

Zoom may be utilized unless prohibited by local guidelines. Telehealth assessments must be consistent with local policies and standards. The requirements for data protection, must be adhered to.

- Provide a script to a local lab for clinical labs required per protocol
- Home visits may be conducted by a trained mobile healthcare professional to perform study assessments e.g. vital signs, body system assessment, clinical labs draws, review/collection of study materials
- For subjects intending to immediately transition into ELARA, the week 12 (NEPTUNE EOT) visit may be considered as ELARA Baseline if ELARA protocol criteria are met.
- Unused IP should be shipped back to site for reconciliation.

- 
- Ensure subject diaries are collected and reviewed appropriately.
 - If any patient is enrolling into the ELARA study immediately after week 12 visit, EOS week 14 visit (over the phone) should be completed prior to enrollment into ELARA

If at any time during the conduct of the NEPTUNE study /a subject contracts COVID-19 infection or any reportable infectious disease, the local health authority requirements regarding treatment/reporting/quarantine should be followed. The event should be reported as an AE/SAE and the investigator should determine if study treatment should be continued, temporarily interrupted, or discontinued.

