3.9.2 Clinical Laboratory Evaluation

A list of clinical laboratory tests is given below:

Hematology	
 - Hematocrit - Hemoglobin - Red blood cell count - Mean corpuscular volume - Mean corpuscular hemoglobin - Mean corpuscular hemoglobin concentration - Reticulocytes - White blood cell count 	
 - Neutrophils (% and count) - Lymphocytes (% and count) - Monocytes (% and count) - Eosinophils (% and count) - Basophils (% and count) - Platelet count - Prothrombin time - Partial thromboplastin time - International normalization ratio
Clinical Chemistry	
 - Albumin - Alkaline phosphatase - Blood urea nitrogen - Gamma-glutamyl transferase - Calcium - Creatinine - Glucose - Cholesterol, high-density lipoprotein [calculated] - Cholesterol, low-density lipoprotein [calculated] - Cholesterol, homogenous low-density lipoprotein - Triglycerides 	
 - Magnesium - Phosphate - Potassium - Alanine aminotransferase - Aspartate aminotransferase - Lactate dehydrogenase - Sodium - Chloride - Total bilirubin - Direct bilirubin - Total protein - Uric acid - Creatine phosphokinase
Pregnancy Testing¹	
 - Serum β-hCG or urine pregnancy testing for female subjects who have experienced menarche 	

¹ Pregnancy testing parameter will be listed only.

Continuous laboratory data will be examined for trends using descriptive statistics of observed values and changes from baseline to each planned post-baseline visit. These data will also be categorized as low, normal or high based on the reference ranges of the central/local laboratory. Frequencies and percentages will be presented for the shifts in these categories from baseline to each post-baseline visit (i.e., low to normal, low to high, high to low, etc.) for all applicable laboratory parameters listed above. The analyses will be performed using the SS and presented by treatment group.

A separate listing for all clinically significant laboratory abnormalities will be provided.

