4.1 Derived Endpoints and Data Handling

4.1.1 Handling of Repeated Assessments

If multiple results are reported for an assessment at the same post-baseline visit, then the first record will be used in analysis.

[figure not shown]

[figure not shown]

[figure not shown]

[figure not shown]

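### Where a scheduled Week 6 or Week 12 record exists, unscheduled laboratory, vital-sign and ABC-I results in the same window stay out of the by-arm tables, and no worst post-baseline summary is planned

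*SAP*

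**What the plan says.** **Scope.** SAP 3.1.8 states: "Unless otherwise specified, the following analysis visit rules will be implemented for all endpoints". Part of the text that follows is blacked out. The visible exception is the seizure diary, and the sections cited for separate window computations are 3.8.3, 3.8.4 and 3.9.6. The laboratory (3.9.2), vital-sign (3.9.3) and ABC-I (3.9.5) sections are not among them and set no selection rule of their own.

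**Mapping.** For unscheduled visits and early end-of-treatment visits, "assessments will be mapped according to the analysis visit windows in Table 2 for primary summarization and analysis". The Week 6 window is "≥Day 22 - ≤Day 64" (target Day 43). The Week 12 window is Day 65 to Day 92 (target Day 85). Days 2-8 and 9-21 belong to the two phone contacts.

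**Selection.** "If a record exists for the nominal time point, that record will be selected for analysis". Failing that, the record closest to the target day is taken. The earliest is taken only on a tie, and this tie rule does not apply to Weeks 12 and 14. SAP 4.1.1 has a separate rule for repeats at one visit: "If multiple results are reported for an assessment at the same post-baseline visit, then the first record will be used in analysis".

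**Tables.** For laboratory data, "Frequencies and percentages will be presented for the shifts in these categories from baseline to each post-baseline visit". Vital signs and the ABC-I are also summarized by visit. The SAP text available contains no worst-value or any-time post-baseline table. SAP 3.3.6 defines the laboratory and vital-sign endpoints as change and shift, and the ABC-I endpoint as change, from baseline to every post-baseline assessment.

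**Unscheduled visits.** Under Study Design in the protocol synopsis, "subjects may be evaluated at unscheduled clinic visits for reasons related to subject safety". Suicidality is evaluated at these visits and safety laboratory tests are optional. Protocol Section 13 adds that, if site visits become possible between Week 6 and Week 12, the child should have an on-site unscheduled visit and "all safety assessments should be completed at this visit".

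**The concern.** The plan foresees extra safety assessments and then, for a child who also attends the scheduled visit, leaves them out of the numeric comparison between arms. Take a liver enzyme that is normal at baseline, high on an unscheduled Day 30 draw and normal on Day 43. The shift table shows normal to normal. A result obtained because a child was unwell is plausibly more likely to be abnormal than a routine one, so leaving such results out would move the tables toward showing no shift. Shift tables are useful because they show category changes that do not depend on a judgement of clinical significance, and this is the information lost. The tables also fall short of the SAP's own endpoints, which refer to every post-baseline assessment and not to one per window.

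**Working it through.** The documents state no figure to reproduce. The check applies the SAP 3.1.8 rules to one unscheduled record placed on each study day.

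**Inputs (SAP 3.1.8, Table 2).** Week 6 window Day 22-64; Week 12 window Day 65-92; phone windows Day 2-8 and Day 9-21; target days 43 and 85. I read the nominal record as the one from the scheduled visit, which is how the nominal-visit supportive analysis at the end of 3.1.8 uses the term. Scheduled visits are placed on their target days.

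**Day counts.**
- Week 6 window: 64 − 22 + 1 = 43 days, or 42 without Day 43.
- Week 12 window: 92 − 65 + 1 = 28 days, or 27 without Day 85.
- Phone windows: Day 2 to Day 21 = 20 days.
- Total: 42 + 27 + 20 = 89 possible days.

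**Fate of one unscheduled record.**

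| Scheduled records present | Left out | Used as the Week 6 or Week 12 value | In a phone window |
|---|---|---|---|
| Both | 42 + 27 = 69 of 89 (77.5%) | 0 | 20 |
| Week 12 only | 27 of 89 (30.3%) | 42 (Week 6) | 20 |
| Week 6 only | 42 of 89 (47.2%) | 27 (Week 12) | 20 |
| Neither | 0 | 42 + 27 = 69 | 20 |

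**Pandemic on-site visit.** It can fall on Days 44-84, which is 41 days. With both scheduled records present, its result is left out on 41 of 41 days. If a parameter has no Week 6 record, the on-site result becomes the Week 6 value on Days 44-64 (21 of 41). On Days 65-84 (the other 20) it is left out in favour of the scheduled Week 12 record.

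**Days 2-21.** An unscheduled result here is normally the only record in its phone window, so the rule selects it. Whether it is then tabulated is unclear. SAP 3.9.2 limits the laboratory change summary to planned visits, but its shift tables, and those of 3.9.3, refer to post-baseline visits without that word.

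**Children affected (illustration).** Assume that a proportion p of the 90 randomized children have one unscheduled draw, uniform over the 89 days, and that both scheduled records are present. The expected number left out is 90 × p × 69/89:
- p = 5%: 4.5 × 0.775 = 3.5
- p = 10%: 9 × 0.775 = 7.0
- p = 20%: 18 × 0.775 = 14.0

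None of these rates is in the documents.

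**The case against.** The strongest reply is that the results of most clinical concern are not lost. Protocol 6.4.1.4 requires abnormal laboratory and other safety results to be recorded as adverse events when the investigator judges them clinically significant. They then enter the by-arm TEAE tables of SAP 3.9.1.2. Individual values remain in subject listings, and the IDMC reviews individual and aggregate safety data. The safety analysis is wholly descriptive, and the primary and key secondary tests are untouched. This stands, and it confines the point to the numeric tables. It does not close the gap: an abnormality not judged clinically significant survives only in listings, which summarize nothing by arm.

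Four stronger readings are tempting, and the documents do not support them:
- **That unscheduled results drop out altogether, or that the first record in a window wins.** They are mapped in, and the closest one is used when the scheduled record is missing. The first-record rule in 4.1.1 concerns repeats at the same visit.
- **That titration-phase results (Days 2-21) are excluded.** The SAP is unclear on this.
- **That the tables are biased in favour of OV101.** One rule applies to both arms. A larger loss on OV101 would require that OV101 prompts more unscheduled visits with abnormal findings, which nothing in the documents shows.
- **That every removed record was prompted by illness.** The pandemic visit is triggered by site access. At ordinary unscheduled visits laboratory tests are optional and vital signs are not named, so the vital-sign part rests mainly on Protocol Section 13.

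A worst-value table also has a weakness of its own: the arm with more extra visits has more chances to show an abnormality. That is a reason to show the number of visits beside it, not to omit it.

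**Conclusion.** The point holds in a limited form. Whenever the scheduled record exists, SAP 3.1.8 keeps unscheduled laboratory, vital-sign and ABC-I results on Days 22-92 out of the by-arm by-visit tables, and nothing else in the plan summarizes them numerically by arm. Including the ABC-I rests on its being the suicidality instrument (Protocol 6.4.2.1) and on suicidality being evaluated at unscheduled visits. The loss matters most for abnormalities not judged clinically significant. The number of children is unknown, and the range of about 3.5 to 14 depends wholly on the assumed 5-20% rate and on both scheduled records being present. No efficacy conclusion is affected. The remedy is cheap and recovers safety information already collected, so it should be made before database lock.

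**What to change.** - In SAP 3.9.2 and 3.9.3, add by-arm shift tables from baseline to the lowest and to the highest post-baseline category.
- In SAP 3.9.5, add the by-arm change from baseline to the worst post-baseline ABC-I score.
- Base these on all records from first dose to the end of the TEAE window, scheduled and unscheduled, from central and local laboratories. SAP 3.9.2 already categorizes by central or local reference range, so the categories can be combined.
- State in 3.1.8 and 4.1.1 that the one-record rules govern by-visit summaries only, and say whether Day 2-21 results appear in any by-visit table.
- Show the number of unscheduled assessments by arm beside the new tables, so that unequal opportunity to detect an abnormality is visible.

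The cost is SAP wording and a few extra tables from data already collected, with no new visits or samples.

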3.2 Analysis Populations and Subgroups

3.2.1 Definition of Analysis Populations

The following analysis sets, with the exception of the Intent-to-treat and Safety Set, will only include subjects 4 to 12 years old (inclusive) at screening. The baseline and safety analyses for subjects 2 to 3 years old (inclusive) at screening will be conducted separately.

Intent-to-Treat Analysis Set

The intent-to-treat set (ITT) will consist of all subjects who are randomized (subjects aged 4 to 12 years old (inclusive) or enrolled (subjects aged 2 to 3 years old (inclusive) and meet all inclusion and exclusion criteria), whether or not study drug is received. Subjects aged 4 to 12 years old (inclusive) will be analyzed according to their randomized treatment.

Full Analysis Set

The full analysis set (FAS) will include all subjects aged 4 to 12 years old (inclusive) who are randomized, receive at least 1 dose of study drug, and have at least 1 post-baseline assessment of the primary efficacy endpoint. The FAS will be used for efficacy analyses based on the randomized treatment for each subject.

Per Protocol Set

The per protocol set (PPS) is a subset of the FAS that includes subjects who complete the Week 12 CGI-I-AS assessment (with appropriate visit mapping as shown in Table 2) and have no major protocol deviations that are deemed to impact efficacy. These violations include but are not limited to violations of inclusion/exclusion criteria deemed to impact efficacy, inadequate study drug compliance over the dosing period as determined from the dosing information in the eCRF, usage of prohibited concomitant medications, and incorrect randomization. Additionally, other relevant protocol deviations, such as early termination or interruption of treatment, may be identified for review.

Prior to database lock and unblinding, there will be a meeting to review all protocol deviations to determine PPS exclusions. The threshold for percent compliance that would be considered inadequate and would result in exclusion from the PPS will also be determined in this meeting following review of the relevant compliance

information. The PPS will be used for efficacy analyses based on the randomized treatment for each subject.

Safety Set

The safety set (SS) will consist of all subjects in the ITT who receive at least 1 dose of study drug and will be used for safety analyses. The safety analyses will be based on the treatment that was actually administered to each subject and will be conducted separately for subjects 2 to 3 years old (inclusive) and subjects 4 to 12 years old (inclusive).

3.2.2 Definition of Subgroups

Subgroups will be defined by age group (randomization stratification variable: age 4 to 8 years versus age 9 to 12 years) and by region (randomization stratification variable: US versus outside US).

3.3 Analysis Endpoints

3.3.1 Primary Efficacy Endpoint

- The CGI-I-AS score at Week 12

3.3.2 Key Secondary Efficacy Endpoint

[figure not shown]
- CGI-I-AS response (at least minimally improved) defined as CGI-I-AS score of 1, 2, or 3 at Week 12
- CGI-I-AS response (at least much improved) defined as CGI-I-AS score of 1 or 2 at Week 12

[figure not shown]
The key secondary endpoints will be utilized to fulfill a recommendation of EMA for a responder analysis.

3.3.3 Other Secondary Efficacy Endpoints

- VABS-3 assessment scores, change from Baseline to Week 12
 - Total Score (Adaptive Behavior Composite Score)
 - Communications domain and its subdomains
 - Socialization domain and its subdomains
 - Daily Living Skills domain and its subdomains
 - Motor Skills domain and its subdomains
 - Maladaptive Behavior subdomains
- CGI-S-AS scores, change from Baseline to Week 12
 - The CGI-S-AS symptoms overall score
 - The CGI-S-AS domain scores

[figure not shown]

3.3.6 Safety Endpoints

- Incidence of adverse events
- Change in clinical laboratory parameters from Baseline to each post-baseline assessment
- Shift in clinical laboratory parameters from Baseline to each post-baseline assessment
- Change and shift in vital sign measurements from Baseline to each post-baseline assessment

- Change in suicidality assessment (ABC-I) from Baseline to each post-baseline assessment. The ABC-I will serve as a surrogate measure for suicidality
- Percent change in seizure frequency (collected in seizure diary) per 28 days from Baseline to each post-baseline time point

